Check-ins (remote or in person, as applicable/convenient) will be conducted twice a week for the first three weeks. Any issues with treatment will be recorded on Appendix F Weekly Check-In CRF. In addition, once a week, for the first 3 weeks, the DVPRS with supplemental questions will be administered.

A chart review will be completed at 3 months to ensure that all PT visit information is recorded in study documentation (Appendix G). A medical record review will be completed to obtain this information. A study visit is not required on behalf of the participant.

A self-report battery will be obtained for each Achilles tendon, regardless of treatment, using Appendix H Follow-Up Data Collection CRF, which will be administered at 3-weeks, 6-weeks, 3-months, and 6-months post-intervention start.

Participants will complete the ultrasound imaging, heel raise test, ankle strength and ROM, hopping test, and be asked to complete a patient satisfaction and expectation survey at the 3-month and 6-month timepoints.

Participants will be evaluated for adverse events at each follow-up time point and any complications will be documented.

Data may be captured in person or remotely (e.g., entered directly into REDCap using a personalized coded link with no log-in required, verbally over the phone with a study team member, etc.). Reminder phone calls, texts, and/or emails will be sent to participants at their preferred contact method indicated on the Intake Form (Appendix B).

Please see the Study Flow Diagram (Appendix L) for a visual representation of the study procedures.

Missed Appointments and Study Removal:

If a participant misses a scheduled appointment, they will be contacted to reschedule in order to maintain the treatment plan of their assigned study treatment group. In the event that a participant misses an appointment, study staff will make one attempt to reschedule each day on three separate days (for three total attempts to reschedule). If the participant cannot be reached or does not respond/reschedule, they will be removed from the study due to non-compliance.

10.2 Data Collection:

Describe all the data variables, information to be collected, the source of the data, and how the data will be operationally measured.

Questionnaires:

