List the statistical methods to be used to address the primary and secondary objectives, specific aims, and/or research hypotheses. Explain how missing data and outliers will be handled in the analysis. The analysis plan should be consistent with the study objectives. Include any subgroup analyses (e.g., gender or age group). Specify statistical methods and variables for each analysis. Describe how confounding variables will be controlled in the data analysis

Descriptive statistics will report location and scale in terms of mean and standard deviation for normally distributed variables, median and interquartile intervals for ordinal metric variables, and in terms of proportion and size for categorical variables.

Outliers will be removed if determined to be erroneous based on relevant clinical expertise. Data will be analyzed on a complete-case intention-to-treat (ITT) basis. Confounding will be principally controlled by randomization. In order to increase the precision of our estimates, we may also statistically adjust for patient demographics and relevant clinical variables if warranted based on statistical best practices.

Methods to be used for the Primary Aim: Time-to-event analyses (return to activity) will use survival analysis. All other outcome measures (including our primary outcome measure (VISA-A) and other aforementioned secondary outcome measures such as functional testing, ultrasound measures, etc.) will be analyzed using generalized additive models predicting change in each outcome measure by treatment group at 3 months. Sensitivity analyses for non-time-to-event outcome measures will be performed to evaluate trends by treatment group and will use longitudinal hierarchical/multilevel models incorporating random effects to account for repeated measures.

Methods to be used for the Secondary Aim: Due to the lack of washout period between initial and cross-over periods, as well as the removal of patient blinding (patients may choose the specific treatment they wish to receive during this final 3-month period), cross-over response will be analyzed as an exploratory aim versus an inferential aim. Due to the exploratory nature of this aim, additional or adjusted analyses may be performed to best explore and evaluate the data collected. Generalized additive models will be used to explore cross-over results and a limited set of measures will be explored (patient satisfaction, functional tests, ultrasound measures).

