Multilevel models will incorporate random effects to account for repeated measures, using distribution families and link functions appropriate for the outcomes of interest, determined using QQ plots analyzed for best model fit. All statistical analyses will be performed using the R Programming language.

11.2 Sample Size:

We are requesting to enroll 160 total participants (40 per initial treatment arm) after adjusting for screen failures and attrition for a final sample of at least 112 (28 per initial treatment arm). 35 patients in each initial treatment group (140 patients total) will achieve 90% power to detect an effect size of 16 points. 30 patients in each initial treatment group (120 patients total) will achieve 90% power to detect an effect size of 17 points. 25 patients in each initial treatment group (100 patients total) will achieve 90% power to detect an effect size of 18 points. Effect size for the purpose of power calculations was defined as the difference between VISA-A at 3 months between PT only and PT + Additional Treatment (assumptions were based on PT + PBMT due to availability of comparable historical research), with statistical significance defined as $\alpha = 0.05$.

11.3 Total number of subjects requested (including records and specimens):

160

11.4 If you are recruiting by study arm, please identify the arms of the study and how many subjects will be enrolled in each arm

Across all performance sites, up to 160 participants will be randomized 1:1:1:1 to the four initial treatment arms (40 participants per arm)

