11.5 Please provide a justification for your sample size

Power was calculated using repeated Monte Carlo Markov Chain simulations predicting 3-month VISA-A between treatment arms, and sourced assumptions of mean and spread from Tumilty et al (2016). MCID was considered to be a 6.5 point difference in VISA-A¹⁴.

11.6 Data Analysis Plan: Complete description: Background, Objectives, Design, Step by Step how the project is going to be done, Data analysis plan:

Outliers will be removed if determined to be erroneous based on relevant clinical expertise. Data will be analyzed on a complete-case intention-to-treat (ITT) basis. Confounding will be principally controlled by randomization. In order to increase the precision of our estimates, we may also statistically adjust for patient demographics and relevant clinical variables.

Methods to be used for the Primary Aim: Time-to-event analyses (return to activity) will use survival analysis. All other outcome measures (including our primary outcome measure (VISA-A) and other aforementioned secondary outcome measures) will be analyzed using generalized additive models predicting change in each outcome measure by treatment group at 3 months. Sensitivity analyses for non-time-to-event outcome measures will be performed to evaluate trends by treatment group and will use longitudinal hierarchical/multilevel models incorporating random effects to account for repeated measures. Analyses under the primary aim will use the initial 3-month cohort only.

Methods to be used for the Secondary Aim: Due to the lack of washout period between initial and cross-over periods, as well as the removal of patient blinding (patients may choose the specific treatment they wish to receive during this final 3-month period), cross-over response will be analyzed and treated as an exploratory aim versus an inferential aim. Due to the exploratory nature of this aim, additional or adjusted analyses may be performed to best explore and evaluate the data collected. Generalized additive models will be used and a limited set of measures will be explored (patient satisfaction, functional tests, ultrasound measures).

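### The primary VISA-A analysis is complete-case under an ITT label: it leaves out interim scores and makes baseline adjustment optional, at a modest cost in precision and, only under selective loss, some bias

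*Combined protocol and SAP*

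**What the plan says.** Sections 11.1 and 11.6 carry the same rule: "Data will be analyzed on a complete-case intention-to-treat (ITT) basis". Section 11.1 asks how missing data will be handled, and this sentence is the only answer. No missing-data assumption, imputation or analysis for informative loss is given.

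All outcomes other than time-to-event ones, VISA-A included, "will be analyzed using generalized additive models predicting change in each outcome measure by treatment group at 3 months". Adjustment for demographics and relevant clinical variables is optional, and baseline VISA-A is not named. A longitudinal model appears only in a supporting role: "Sensitivity analyses for non-time-to-event outcome measures will be performed to evaluate trends by treatment group and will use longitudinal hierarchical/multilevel models". Section 11.6 adds: "Analyses under the primary aim will use the initial 3-month cohort only".

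Section 11.2 asks for 160 participants "after adjusting for screen failures and attrition for a final sample of at least 112 (28 per initial treatment arm". Section 11.4 plans 40 per arm.

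On early scores, Section 10.1 (Follow-Up Data Collection) says: "A self-report battery will be obtained for each Achilles tendon, regardless of treatment, using Appendix H Follow-Up Data Collection CRF", which is "administered at 3-weeks, 6-weeks, 3-months, and 6-months post-intervention start". The items kept for 3 and 6 months are listed separately, beginning "Participants will complete the ultrasound imaging, heel raise test, ankle strength and ROM, hopping test, and be asked to complete a patient satisfaction", and VISA-A is not among them. Under Section 13.6, data gathered before withdrawal may be analysed and none are gathered afterwards. Section 10.1 removes participants who cannot be rescheduled after three attempts.

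**The concern.** An ITT analysis keeps everyone who was randomised, in the arm assigned. A complete-case rule keeps only those with a 3-month score, so the label and the rule describe different sets. Because the sentence covers all data, it may restrict the longitudinal sensitivity model too.

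Two costs could follow. One is precision: an unadjusted change score uses baseline inefficiently, and a participant lost after week 6 adds nothing to the estimate even if early scores exist. The other is bias: if those who leave differ in response, and differ in a way that is not the same in each arm, the completers no longer give a fair comparison. Section 11.5 sets the MCID at 6.5 points, and the stakes should be read against that figure.

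**Working it through.** **Inputs from the documents.** 90% power, two-sided 0.05, for 16, 17 or 18 points with 35, 30 or 25 per arm (11.2, 11.6); 40 per arm (11.4); final sample at least 112 of 160 (11.2); MCID 6.5 (11.5).

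**SD.** It is not stated, so it is back-solved: SD = difference × √(n/2) / (1.960 + 1.282).
- 16 × √17.5 / 3.242 = 20.6
- 17 × √15 / 3.242 = 20.3
- 18 × √12.5 / 3.242 = 19.6

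With the t distribution these become 20.4, 20.0 and 19.2. The three power statements therefore agree with one another to within rounding of the effect sizes. SD 19.5 is used below; standard errors scale in proportion.

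**Loss.** 1 − 112/160 = 0.30. This is an upper bound for loss among those randomised, because it includes screen failures, and the pregnancy test falls between consent and randomisation (10.1, 13.3).

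**Correlations (assumed; the documents give none).** Base case: baseline–6 weeks 0.5, baseline–3 months 0.4, 6 weeks–3 months 0.7; for the 3-week score, 0.6 with baseline, 0.75 with 6 weeks and 0.6 with 3 months. Ranges cover ten sets: baseline–3 months 0.2 to 0.6, baseline–6 weeks 0.3 to 0.7, 6 weeks–3 months 0.5 to 0.8.

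**Step 1: precision from baseline adjustment.** With 28 completers per arm and r = 0.4:
- change: 19.5 × √(2 × 0.6) × √(2/28) = 5.71
- adjusted: 19.5 × √(1 − 0.16) × √(2/28) = 4.78

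The large-sample gain is 1 − √((1 + r)/2): 23% at r = 0.2, 16% at 0.4, 11% at 0.6. Simulation at 40 per arm with 30% random loss gives 21%, 15% and 9%. The base-case SEs are 5.74 and 4.87, so the half-widths are 1.96 × 5.74 = 11.3 and 1.96 × 4.87 = 9.5.

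**Step 2: precision from interim scores.** Take the 6-week score alone. Its correlation with the 3-month score given baseline is (0.7 − 0.5 × 0.4) / √(0.75 × 0.84) = 0.63, squared 0.397. Relative to complete-case adjustment, the SE is multiplied by √(1 − 0.397 × (1 − 28/m)), where m is the number per arm with an interim score.
- all have one (m = 40): 6.1% gain
- half of those lost have one (m = 34): 3.6%
- none of those lost has one (m = 28): 0

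With both early scores and all present, simulation gives SE 4.58 and half-width 1.96 × 4.58 = 9.0. Over the correlation sets the gain is 2% to 11% at 30% loss and 1% to 5% at 15%.

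**Step 3: bias.** Let loss in one arm follow a logistic model in the 6-week score (log-odds 1 per SD, 30% lost). Integrating over the normal distribution, the mean 6-week score of completers in that arm shifts by 0.253 SD = 4.9 points. The bias in the 3-month contrast is then about:
- change: (0.7 − 0.5) × 4.9 = 1.0
- complete-case adjusted: (0.7 − 0.4 × 0.5) × 4.9 = 2.5

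Simulated sizes, in points (the sign depends on which arm loses and who leaves):

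| Loss, 30% | Planned change | Complete-case adjusted | Repeated measures, unstructured |
|---|---|---|---|
| Random, or alike in both arms | about 0 | about 0 | about 0 |
| One arm, by 6-week score: base | 0.9 | 2.5 | 0.0 |
| Same: range over the sets | 0 to 2.5 | 1.2 to 3.7 | 0.0 |
| Same, half of dropouts without an early score: base | 1.0 | 2.5 | 1.0 |
| One arm, by the unseen 3-month score: base | 3.0 | 4.2 | 2.5 |

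The base-case bias of the planned analysis is 0.9/5.74 = 0.16 SE. It reaches 0 when baseline and 3 months correlate equally with 6 weeks. At 15% loss the one-arm range is 0 to 1.4. A steeper slope (1.5 per SD) takes the upper end at 30% loss to 3.2. In the high-correlation set the repeated-measures model is slightly worse than the planned analysis in the last two situations: 0.6 against 0.0, and 2.4 against 2.0.

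**Step 4: covariance.** In the one-arm scenario, a random-intercept model with the same mean terms leaves bias of about 0.5 (base) and 1.3 (low-correlation set), against 1.1 and 2.5 for the planned analysis in the same runs. Random effects alone do not deliver the 0.0 in the table.

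**The case against.** The plan has real defences. Most of the precision difference, 11.3 to 9.5, comes from baseline adjustment, which needs no change to the complete-case rule and which Section 11.1 already permits in order to gain precision. Only 9.5 to 9.0 belongs to the interim scores. The sample size already budgets for 28 per arm. A longitudinal model is prespecified, if only as a sensitivity analysis. All of this stands, and it limits the size of the point. It does not justify the label, nor leaving a known precision gain to a later choice.

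Stronger readings are tempting, and the documents do not support them:
- *The primary result will be biased.* Different loss rates by arm do not by themselves cause bias; loss must relate to outcome differently by arm. Section 13.6 lists causes unrelated to arm, such as military need and loss of entitlement to care. Sections 10.1 and 13.2 give reasons to stay: a choice of another arm at 3 months, and payment at follow-up visits. Visit burden does differ (check-ins for PT alone may be virtual, while the PBMT arm has six in-person treatment visits), but that makes unequal rates plausible, not selective loss. Bias near 5 points needs arms to lose in opposite directions, for which nothing in the text speaks.
- *Thirty percent of randomised participants will be lost.* The figure includes screen failures.
- *Promoting the longitudinal model as written cures the problem.* Section 11 plans random-effects models for trends, which Step 4 shows is not enough.

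**Conclusion.** The point holds in a limited form. The analysis set is mislabelled and the handling of missing VISA-A scores is underspecified. If the optional adjustment is not used, leaving out baseline VISA-A gives an interval wider than the same data allow. Interim scores offer a smaller and conditional gain. Bias in the planned analysis is a possibility rather than a finding, and in the base case it is small beside both its own SE and the 6.5-point MCID. Adjusting for baseline within complete cases is not a full answer, since it improves precision but enlarges bias when loss is selective.

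These sizes rest on a back-solved SD, assumed correlations and dropout slopes, 30% loss as an upper bound, and VISA-A being in the 3- and 6-week battery. That last point is inferred from Section 10.1; Appendices H and T were not available to this review. This should be fixed because the remedy is cheap, not because the trial is unsound without it.

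**What to change.** 1. In 11.1 and 11.6, make the primary VISA-A analysis a likelihood-based repeated-measures model on all randomised participants as randomised, using every available score at baseline, 3 weeks, 6 weeks and 3 months. Specify categorical visit, arm-by-visit terms, baseline in the outcome vector with arms constrained equal, and an unstructured covariance rather than a random-intercept trend model. The estimate is the 3-month arm contrast; 6-month data stay out.
2. State that the complete-case rule does not apply to this model, and replace the label with the actual analysis set.
3. Keep the complete-case 3-month analysis and add a delta-adjusted analysis, both as sensitivity analyses.
4. Report loss by arm and last completed visit.
5. Confirm that VISA-A is in the early battery. If only the 6-week score exists, almost all of the interim gain remains (6.1% against 6.3% in large samples, base case). If neither exists, use the constrained baseline and 3-month model, which keeps the baseline-adjustment gain.
6. Optionally, say in 10.1 that participants who miss appointments but have not withdrawn are still asked for the 3-month VISA-A by the existing remote route. The yield is unknown.

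Items 1 to 5 cost SAP wording only; item 6 needs a short protocol amendment. The downside is reliance on missing-at-random: when dropouts have no interim score, or loss depends on the unseen 3-month score, the model gives little benefit and can do slightly worse than the planned analysis.

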In order to standardize the loading program for study participants, we will provide all participants with an at-home exercise program designed by [name] for progressive Achilles tendon loading.¹⁰ This will be completed alongside the standard of care PT they are receiving. Activities including running will be allowed as tolerated following published guidelines by [name].^{11,12,13} This treatment protocol consists of four phases that last 12 weeks to 6 months. The first phase includes a circulation exercise and various forms of toe raises. Phase two increases the intensity of the various toe raise exercises, and in phases three and four plyometric activities are added. Participants are expected to exercise every day for the first 12 weeks and then can decrease to 2-3 times per week thereafter, up to 6-months. The at-home exercise program instructions are outlined in participant handout Appendix J Silbernagel Guidelines.

All participants will also follow the University of Delaware Return to Sport protocol for returning to running (Appendix K).

All activities, including home exercises and running, pain, and pain medications taken, will be recorded by the participant daily in a log (Appendix E).

If a study participant has bilateral AT, the leg with the most severe symptoms [determined by the Victorian Institute of Sports Assessment – Achilles (VISA-A) in the Data Collection CRF; more information regarding the VISA-A in Section 10.2] will be chosen as the primary data point for the study. However, both legs will be treated consistently according to the treatment group the participant was randomized into.

Physical Therapy (PT) Only Arm

Participants in the PT only arm will follow the PT program outlined above. Twice a week for three weeks, a team member will check-in with the participants to ensure physical therapy exercise adherence, and response to treatment. During the second check-in of the week, the study team member will also ensure the participant is keeping their activity/medication/pain log; the study team member will also deliver the DVPRS with supplemental questions. (See Appendix F for Check-in Data Collection CRF). These check-ins may occur virtually or in-person.

In Part 1, the *physical therapy only* arm requires 8 visits. The participants will complete 2 check-in visits each week (remote or in person), for three weeks. Follow-up data will be collected at 6 weeks (virtual or in-person) and at 3 months (in-person).

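### The primary VISA-A model analyses change by arm and need not include baseline VISA-A, so precision may be lost and the model is not fixed in advance.

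*Combined protocol and SAP*

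**What the plan says.** Section 11.1 states that the primary outcome, VISA-A, and the secondary outcomes other than time to return to activity "will be analyzed using generalized additive models predicting change in each outcome measure by treatment group at 3 months". Section 11.6 gives the same model. Treatment group is the only term specified.

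On covariates, section 11.1 says: "we may also statistically adjust for patient demographics and relevant clinical variables if warranted based on statistical best practices". Section 11.6 repeats this without the closing condition: "In order to increase the precision of our estimates, we may also statistically adjust for patient demographics and relevant clinical variables". Neither section names a variable or says when the choice will be made. The form's own instruction at the head of 11.1 is: "Specify statistical methods and variables for each analysis".

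Multilevel models that use the repeated measures are planned, but both sections label them sensitivity analyses.

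Two further places bear on the point. Section 11.2 gives a final sample of at least 112, or 28 per arm, and section 11.5 describes the power work as "simulations predicting 3-month VISA-A between treatment arms". In section 10.1, for bilateral disease, the leg with the more severe symptoms on VISA-A "will be chosen as the primary data point for the study".

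**The concern.** Analysing change subtracts the baseline score with a coefficient fixed at 1. Putting baseline in the model lets the data estimate that coefficient, and in large samples the result is never less precise. The plan gives precision as its reason for possible adjustment, yet leaves the most obvious candidate, the baseline of the primary outcome, to a later decision. That value must be recorded in any case to compute change.

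Two things are at stake. The first is precision in a trial that may finish with 28 per arm and whose stated detectable differences are 16 to 18 points, against a minimal important difference of 6.5 (sections 11.2 and 11.5). The second is pre-specification. The primary result could come from the adjusted or the unadjusted model, and if the choice between them depended on the results, the 5% error rate would not hold.

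**Working it through.** **Inputs.** From the documents: 28 per arm, four arms, two-sided alpha 0.05, and 90% power for 16, 17 and 18 points with 35, 30 and 25 per arm. Not in the documents, and so assumed over a range: r, the correlation of baseline with 3-month VISA-A (0.3 to 0.7), and k, the baseline SD divided by the 3-month SD (0.8 to 1.2).

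**The plan's own power figures.** No SD is stated, so they cannot be reproduced independently. Solving SD = d × √(n/2) / (1.960 + 1.282) gives:

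- 35 per arm, 16 points: 20.65
- 30 per arm, 17 points: 20.31
- 25 per arm, 18 points: 19.63

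These agree with one SD near 20, allowing for rounding to whole points and for simulation. Nothing here shows the 90% to be wrong.

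**Variance ratio.** Take the 3-month variance as 1. Unadjusted change has variance 1 + k² − 2rk. The baseline-adjusted residual variance is 1 − r². The ratio is

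(1 + k² − 2rk)/(1 − r²) = 1 + (k − r)²/(1 − r²),

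which is never below 1 and equals 1 only at r = k. For example, at k = 0.8 and r = 0.3 it is 1 + 0.25/0.91 = 1.27.

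| k | r = 0.3 | r = 0.5 | r = 0.7 |
|---|---|---|---|
| 0.8 | 1.27 | 1.12 | 1.02 |
| 1.0 | 1.54 | 1.33 | 1.18 |
| 1.2 | 1.89 | 1.65 | 1.49 |

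**Interval width and equivalent n, before the cost of adjusting.** Width is multiplied by the square root of the ratio, and the equivalent n is 28 divided by the ratio. Each cell lists r = 0.3 / 0.5 / 0.7.

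| k | Intervals wider by | Equivalent n per arm |
|---|---|---|
| 0.8 | 13 / 6 / 1% | 22.0 / 25.0 / 27.5 |
| 1.0 | 24 / 15 / 8% | 18.2 / 21.0 / 23.8 |
| 1.2 | 37 / 29 / 22% | 14.8 / 16.9 / 18.8 |

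**In VISA-A points.** Assume the back-solved SDs of about 19.6 to 20.7 describe the unadjusted 3-month score, with k = 1. The difference detectable with 90% power at 28 per arm is 3.242 × √(2/28) × residual SD. The residual SD is SD × √(2(1 − r)) for unadjusted change and SD × √(1 − r²) with adjustment.

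| r | Unadjusted change | Baseline-adjusted |
|---|---|---|
| 0.3 | 20.1 to 21.2 | 16.2 to 17.1 |
| 0.5 | 17.0 to 17.9 | 14.7 to 15.5 |
| 0.7 | 13.2 to 13.9 | 12.1 to 12.8 |

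**Cost of adjusting.** Chance baseline imbalance multiplies the variance by about 1 + 1/(N − arms − 2). This is 1 + 1/106 = 1.009 for one four-arm model (N = 112) and 1 + 1/52 = 1.019 for a two-arm fit (N = 56). A smooth with 3 degrees of freedom costs about 3% and 6%.

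**Small-sample check.** Simulation with 6,000 runs per setting, normal data, no treatment effect, k = 1 and four arms of 28 gave variance ratios of 1.54 / 1.31 / 1.14 for linear adjustment and 1.52 / 1.28 / 1.12 for a cubic with 3 degrees of freedom. At k = r = 0.8 the ratios were 0.99 and 0.97, which is the cost of adjusting when there is nothing to gain. Each single analysis kept its type I error at 4.5 to 5.4%.

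**Choosing between the two models on the result.** Under the null the two test statistics have correlation 1/√ratio, which is 0.806 / 0.866 / 0.922 at k = 1. From the bivariate normal, the chance that at least one gives p < 0.05 for a single contrast is 7.8 / 7.3 / 6.8%. Over k = 0.8 to 1.2 it runs from 5.7% to 8.2%.

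**The case against.** The plan permits adjustment for precision, and baseline VISA-A fits naturally among clinically relevant variables. A generalized additive model with group as its only term has no smooth, so naming that model suggests continuous covariates were intended. The multilevel sensitivity analyses would help to expose a result that depends on the unadjusted model. The size of any loss is unknown: with k = 0.8 and r = 0.7 it is 2%. The error-rate point is hypothetical, since inflation requires choosing because of the result, and nothing in the plan says that will happen.

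Much of this is fair as to weight. The figures are illustrative, and the 5.7 to 8.2% covers one choice between two models for one contrast. It neither bounds an open covariate list nor predicts what the team will do. But permission is not a commitment, an inferred intention is not a specified model, and sensitivity analyses do not define the primary result.

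One qualification works against the plan. The analysis is complete-case, and 112 of 160 are expected to remain. Randomization protects the randomized set, not the completers. If loss depends on baseline differently by arm, unadjusted change can be biased where a baseline-adjusted model is not. In an illustrative simulation (r = 0.5, about 30% loss, baseline-dependent in one arm) the bias was about 0.1 SD unadjusted and about zero adjusted.

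**Conclusion.** The concern holds. As written, the primary model need not include baseline VISA-A, and whether it does is left open. With complete outcome data both analyses estimate the same between-arm difference, so the issue is precision and pre-specification.

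Over the assumed range the variance penalty of unadjusted change runs from 2% to 89%, and from 18% to 54% if the two SDs are equal. It vanishes at r = k. These figures rest on assumed r and k, and the conversion to points also rests on an SD back-solved from the plan's power statements. The direction does not depend on those values: in large samples adjustment is never less precise, and at 28 per arm the most a linear term can cost is about 1 to 2% of variance. This should be changed, but the trial remains valid without it.

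**What to change.** In sections 11.1 and 11.6, make baseline VISA-A of the index leg a mandatory covariate in the primary model, either as a linear term or as a smooth whose form is fixed in advance. The outcome may stay as change or become the 3-month score. With a linear baseline term and identity link, the treatment effect and its standard error are identical; a numerical check agreed to within 1e-14. The same term would therefore tie the analysis to the 3-month difference used for power in section 11.2.

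Apply the same rule to the other continuous outcomes with a baseline value, since the same sentence governs them. Any further covariate should be listed before outcome data are reviewed, with one wording in both sections. When 11.2 and 11.5 are next revised, state the SD and correlation assumed and whether the simulation included baseline.

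The cost is SAP wording, one degree of freedom and about 1 to 2% in variance for a linear term (about 3 to 6% for a smooth with 3 degrees of freedom). No new data are needed.
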